Retrograde analysis of data of all patients presented to Aboul Reesh uveitis clinic taking biologics from January 2017- January 2020. In our hospital, the rationale for using biologics was a high frequency of sight-threatening, frequent recurrences of uveitis or intolerance to steroids or other immunosuppressive drugs, with severe adverse reactions.

Sample size:

It is expected to review 250 patients files of Aboul Reesh uveitis clinic to find all JIA patients with ocular inflammation treated with biologics.

Inclusion criteria

1. Both genders
2. Age up to 16 years
3. Diagnosed JIA according to rheumatological criteria with ocular affection
 - Any type of arthritis (oligoarticular, polyarticular, systemic onset, ocular JIA)
 - ANA positive or negative
4. Uncontrolled uveitis or frequent relapses

Exclusion criteria:

1. Patients without definitive diagnosis as JIA

2. JIA patients on biologics without ocular affection (for systemic control) or with uveitis controlled without the use of biologics
4. Patients without adequate duration for follow-up (less than 3 months) or lost follow up data
5. Patients without available data prior to the start biologics (to compare control of the uveitis)

Methodology

Data will be obtained from by retrospective analysis of all files of patients with JIA from the Abou El Reesh ophthalmology outpatient clinic.

The patients with ocular inflammation treated by biologics will be further analyzed.

The data analyzed will divided into pre and post biologic treatment:

In both we will document-

-Baseline BCVA (in logMar notation)

- Grading of ocular inflammation

(Anterior chamber and vitreous cells were graded as +0.5, +1, +2, +3 and +4 according to the guidelines of the Standardization of Uveitis Nomenclature Working Group)

- Number of relapses in one year

- Development of sight threatening complication

- Dose and frequency of systemic, regional and topical steroids

- Other interventions required

Treatment parameters to be analyzed include type, duration and dose of biologic agent used, time taken to reach inflammation control, adverse effects, and time taken to develop those adverse effects.

Improvement or worsening of activity of inflammation was assessed according to the Standardization of Uveitis Nomenclature Group's directions (2 step improvement or worsening of cells/flare)

Treatment was determined as efficacious if one of the following was fulfilled:

1. No relapses or decrease in the number of relapses

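### Patients enter for active disease and are compared with an undefined pre-biologic year, so a large share, possibly most, of those selected for frequent relapses would show a decrease without any drug effect

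*Combined protocol and SAP*

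**What the plan says.** Item 4 of the Inclusion criteria requires "Uncontrolled uveitis or frequent relapses". Neither term is defined and no threshold is given. Under Population of study & disease condition, the hospital's reasons for using a biologic are sight-threatening disease, "frequent recurrences of uveitis or intolerance to steroids or other immunosuppressive drugs, with severe adverse reactions". The Exclusion criteria remove patients "with uveitis controlled without the use of biologics", those with no data from before the biologic, and those with under 3 months of follow-up.

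Methodology gives the comparison: "The data analyzed will divided into pre and post biologic treatment". The items recorded on both sides include "Number of relapses in one year". There is no control group. Treatment counts as efficacious if any one of three criteria is met, and the first is "No relapses or decrease in the number of relapses". No minimum fall is set. The Statistical analysis plan lists ANOVA, Pearson correlation and chi-square tests and does not mention regression to the mean. No section says which year before the biologic supplies the count.

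**The concern.** A relapse count that is chosen because it is high will, on average, be lower at the next measurement even if nothing has changed. Three features of the plan point the same way. Entry favours patients in a bad period, patients who settled on other treatment are removed, and the patient's own pre-biologic record is the only yardstick. If the yardstick is the year that led to the biologic, the baseline is inflated by selection. Because any decrease is enough for success, ordinary year-to-year variation can be read as response.

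The study's stated purpose is to weigh control of ocular inflammation by biologics against their side effects in children. A high success rate on the relapse criterion could arise with an inactive drug, and no planned analysis would reveal it.

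**Working it through.** **No figure to reproduce.** The plan states no relapse rate, effect size, power or expected response rate. The 250 is a number of files to review. Every rate, shape and threshold below is therefore an assumption.

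**Model with no drug effect.** A patient's yearly rate is gamma-distributed with mean m and shape k. The count X before and the count Y after are independent Poisson counts at that same rate, each over a full year. Entry requires X ≥ c.

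- X is negative binomial with size k and probability k/(k+m).
- Given X = x, the rate is gamma with shape k + x and rate parameter k/m + 1, so the expected Y is (k + x)/(k/m + 1).
- Given X = x, Y is negative binomial with size k + x and probability (k/m + 1)/(k/m + 2).
- Share with a decrease = Σ P(X = x)·P(Y < x | x) / Σ P(X = x), summed over x ≥ c.

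**One case by hand (m = 2, k = 2, c = 3).** P(X = 0), P(X = 1) and P(X = 2) are 0.25, 0.25 and 0.1875, so P(X ≥ 3) = 0.3125. The mean count before, among those selected, is (2 − 0.25 − 2 × 0.1875)/0.3125 = 4.4. The mean after is (2 + 4.4)/(2/2 + 1) = 3.2. Relapses fall by 1.2 a year, or 1.2/4.4 = 27%, with an inert drug. The share with a decrease is 65.7%.

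**Range over m = 1.5 to 2.5 and k = 1 to 8.**

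| Entry on pre-biologic count | Share with fewer relapses, no drug effect |
|---|---|
| 3 or more | 59% (m 2.5, k 1) to 80% (m 1.5, k 8) |
| 2 or more | 55% to 67% |
| Not selected on count | 31% to 40% |

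The last row counts decreases only. The relapse criterion also accepts no relapses, so a patient with none before and none after could pass. On a wider grid (mean 1 to 3; a common rate or shape 0.5 to 4), unselected patients show a decrease in 23–42%, and 42–68% pass if none-before-and-none-after is counted.

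**Mixed entry.** If half enter on 3 or more relapses and half are not selected on count (m = 2, k = 2), the share with a decrease is 0.5 × 0.657 + 0.5 × 0.366 = 51%. Counting none-before-and-none-after gives 0.5 × 0.657 + 0.5 × 0.477 = 57%.

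**A different entry mechanism.** Suppose the biologic starts at the c-th relapse within 12 months (mean rate 1, 2 or 3; a common rate or shape 2 or 1). The share with a decrease over the following year then runs from 19% to 97%. It exceeds 50% in 18 of 27 settings, including every one where the trigger is above the mean rate. It is 19–46% in the 9 settings where the trigger is at or below the mean rate.

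**Earlier baseline.** In the hand-worked case, a year before the selected year has mean 3.2, the selected year 4.4 and the year after 3.2. The rise of 1.2 mirrors the fall of 1.2, and the before/after means are equal once the earlier year is the baseline. Even so, 41% have fewer relapses than in that earlier year, and about 43% meet the relapse criterion once zero-and-zero is counted. With three earlier years averaged, ties become rare and about 49% meet it. Over the range of assumptions, the figure with an earlier baseline is about 42–49%.

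**The case against.** The strongest reply is that the model assumes what the plan does not say. Entry is through uncontrolled uveitis or frequent relapses, and the hospital's reasons for a biologic also include sight-threatening disease and drug intolerance. The Background describes the uveitis as chronic. Persistently active disease need not have a high relapse count, and a patient whose rate is always high has less to regress. The baseline year is not fixed, and every rate used here is assumed. An uncontrolled file review carries some of this bias whatever is done.

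Much of that stands, and it rules out three stronger readings that a reader might infer.

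- That the plan has chosen the selection year as its baseline. It has not; the year is unspecified. The year leading to the biologic is only the natural reading.
- That most of the study's patients would count as responders on an inert drug. This is not shown. The 59–80% applies to those selected on a count of 3 or more. The share entering that way is unknown, and other routes can give figures below half.
- That moving the baseline cures the relapse criterion. It equalises the means, but nearly half would still pass because any decrease counts.

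What the reply does not remove is the direction of the bias. Chronic disease still varies from year to year. With shape 1, where persistent differences between patients are the largest in the main range, 59–66% of those entering on 3 or more relapses still show a decrease. The lack of a control group is accepted here; the choice of baseline window is separate and can be changed within the same files.

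**Conclusion.** The concern holds in a conditional form. Selection on disease activity, an own-record comparator with no fixed window, and a rule that any decrease is success together bias the relapse criterion towards efficacy, and the Statistical analysis plan does nothing about it. A large share, possibly most, of those selected for frequent relapses would meet the criterion without any drug effect: about 59–80% at 3 or more relapses and 55–67% at 2 or more.

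These figures rest on assumed gamma-Poisson rates that stay stable over time, a full year on each side, and the selected year as baseline. They are not estimates for this hospital. The 3-month minimum follow-up set against a one-year count, with no rule for annualising, is a separate source of bias and is not included in them. The point should be fixed before extraction. It is a limit on what the relapse result can show, not a reason to abandon the study.

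**What to change.** 1. Before extraction, state which pre-biologic window supplies the relapse count.
2. Where the file holds it, also extract relapses per patient-year from before the 12 months leading to the biologic. Report it alongside the immediate pre-biologic year, in the same patients.
3. State how many patients have that longer history and how they differ from the rest.
4. Show the change between the two pre-biologic periods beside the post-biologic change. A rise into the last pre-biologic year of similar size to the later fall points to regression to the mean. It is a pointer and not proof, since true worsening before the biologic would also produce a rise.
5. Rest the relapse conclusion on the change in mean rate. The share with any decrease can be reported, with a note on how large it could be by chance.

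The cost is more extraction from files already being opened. The protocol sets no minimum pre-biologic history, so the earlier baseline will exist only for a subset with longer disease, which may not represent patients who started a biologic early. The result may also look less favourable.

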Full Protocol

**Retrospective Analysis of the Use of Biologics for Juvenile Idiopathic
Arthritis Related Uveitis in Abou El Reesh Pediatric Hospital, Cairo
University**

Background and introduction

Juvenile Idiopathic Arthritis (JIA) remains, globally, the most common systemic disorder associated with pediatric uveitis. It accounts for approximately 75% of cases of pediatric anterior uveitis (AU) and affects around 30% of ANA positive JIA patients (regardless their type of arthritis).¹ In a cohort study from the Cairo University Pediatric Hospital, JIA accounted for 39% of all cases of pediatric uveitis (unpublished data).

The uveitis, being asymptomatic, chronic and often severe, leads to complications in a large number of patients. Studies estimate that 28–67% of patients with JIA-associated uveitis develop ocular complications, with 12% developing poor visual outcome. The main causes of poor vision were cataract, band keratopathy and macular edema.²

The only means of improving long term effects of uveitis, is early and aggressive anti-inflammatory treatment.³

The main line of treatment of non-infectious causes of uveitis have been topical and systemic corticosteroids. However, it is well known that their prolonged use often leads to ocular and systemic complications, especially in the pediatric age group.⁴

In 2019, the American College of Rheumatology/Arthritis Foundation recommended that in severe active chronic AU or in the presence of sight-threatening complications, methotrexate (MTX) and a monoclonal antibody TNFi should be administered immediately. This is recommended over MTX as monotherapy. They also recommended that inadequate response to one monoclonal TNFi at standard JIA dose, the dose and or frequency should be increased rather than switching to another monoclonal antibody TNFi.⁵

Immunosuppressive drugs are used as steroid-sparing agents but are not free of complications. They increase the susceptibility of children to infection, may cause organ toxicity, reversible bone marrow suppression and may possibly lead to the development of malignancies.³

Thus, our study aims to analyze the use of biologics in our hospital (Abou el Reesh, Cairo University) for children with JIA in controlling their ocular inflammation, prevention of the development of sight threatening complications and if this outweighs their potential associated side effects.

Patients and methods

Population of study & disease condition

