2. Decrease in dose of topical or systemic steroids
3. Improvement of BCVA of at least two lines

Statistical analysis plan:

All data will be entered into Excel spreadsheets (Microsoft Corporation, Redmond, WA, USA). All statistical analyses will be performed using IBM SPSS version 22.0 software (IBM Corp., Armonk, NY, USA). Descriptive statistics will be summarized as the mean \pm standard deviation for numerical data, frequencies and percentages for categorical data. The ANOVA -test and Pearson moment correlation will be used to compare the means for the numerical data and to identify correlations between them. Chi-square test will be used to compare categorical data. P-values ≤ 0.05 will be considered statistically significant.

References

- 2) Qian Y, and Nisha R. (2010) Juvenile Idiopathic Arthritis Associated Uveitis. *Curr Opin Ophthalmol.* 21(6): 468–472. doi:10.1097/ICU.0b013e32833eab83

Retrospective Analysis of the Use of Biologics for Juvenile Idiopathic Arthritis Related Uveitis in Abou El Reesh Pediatric Hospital, Cairo University

First version, 1st march 2020

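### Exclusion item 4 also governs the adverse-effect analysis: if its 3 months run from the start of the biologic, reactions recorded in children who left follow-up early are not counted

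*Combined protocol and SAP*

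**What the plan says.** - **Exclusion criteria, item 4** excludes "Patients without adequate duration for follow-up (less than 3 months) or lost follow up data". It gives no start point for the 3 months, does not define lost follow-up data, and is not limited to any one analysis.
- **Exclusion criteria, item 5** excludes "Patients without available data prior to the start biologics (to compare control of the uveitis". Unlike item 4, it carries its own reason, which is an efficacy reason.
- **Methodology** draws on "retrospective analysis of all files of patients with JIA from the Abou El Reesh ophthalmology outpatient clinic" and then takes forward one group: "The patients with ocular inflammation treated by biologics will be further analyzed". Among the treatment parameters for that group it lists "time taken to reach inflammation control, adverse effects, and time taken to develop those adverse effects".
- **Background and introduction** states the aim as control of ocular inflammation and prevention of complications, and "if this outweighs their potential associated side effects".
- **Statistical analysis plan** provides means with standard deviations, "frequencies and percentages for categorical data", and a short list of tests. It names no separate set for adverse effects and no tabulation of excluded patients by reason.

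**The concern.** A minimum follow-up makes sense for the before-and-after comparison. Relapses are to be counted over a year, and a child seen for a few weeks after starting a biologic tells us little about relapse. Counting a reaction already written in the file needs no such minimum.

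Because one group serves both purposes, an efficacy requirement also decides whose harms are seen. On the reading that starts the clock at the first biologic dose, entry to the adverse-effect analysis depends on what happened after treatment began. A child who had a reaction in the first weeks and did not return would be ineligible, and the reaction would appear in neither the frequency table nor the onset times. Onset time is the more exposed of the two, since the cases lost are by construction early ones. The comparison of benefit with side effects would then rest on an incomplete count of recorded harms, and nothing in the report would tell the reader so.

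**Working it through.** The plan gives no adverse-effect rate, early-leaver count or computed sample size, so there is no figure to reproduce. The 250 in the Sample size section is the number of files to be screened, not the number of treated children. The check is therefore one of reading, followed by a formula for direction.

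**1. Does item 4 reach the adverse-effect analysis?** It stands among the general exclusion criteria. The Methodology describes one analysed group and lists adverse effects alongside time to inflammation control for it. The Statistical analysis plan makes no exception. So it does.

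**2. Who is affected under each possible start point?**

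| Child | Clock from start of biologic | Clock from first clinic visit |
|---|---|---|
| Long earlier attendance; reaction recorded; leaves follow-up before 3 months on the biologic | Excluded; reaction not counted | Passes the 3-month test; may still fall under lost follow-up data, which is undefined |
| Stops the biologic after a reaction but attends for 3 months or more | Retained; reaction counted | Retained; reaction counted |
| Starts the biologic too late to reach 3 months | Excluded | Depends on earlier attendance |
| No record after the first dose | Excluded; no later record to count | Depends on earlier attendance; no later record to count |

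The loss is confined to the first row, plus any reaction recorded in a late starter. It concerns leaving follow-up, not leaving the drug.

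**3. Could short follow-up be innocent?** Yes. The study window is "all patients presented to Aboul Reesh uveitis clinic taking biologics from January 2017- January 2020". If data end with January 2020 (one reading; no cut-off is stated outright), any start after the end of October 2019 has under 3 months of follow-up for calendar reasons alone. Without counts by reason, these children cannot be told apart from those who left.

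**4. Which way would a percentage move?** Among otherwise eligible starters with any later record, let e be the share removed by item 4, a the recorded adverse-effect risk in those removed, and b the risk in those kept.

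- Risk in the analysed set: b
- Risk in all such starters: e·a + (1 − e)·b
- Difference: e·(a − b)

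The reported percentage is too low if a > b, unchanged if a = b, and too high if a < b. The last is possible, because children observed only briefly have less time in which to have a reaction recorded. The documents supply none of e, a and b, so neither sign nor size follows. One result does not depend on the sign: whenever a > 0, recorded reactions are left out of the count, even where the percentage is unchanged.

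**The case against.** The strongest reply is that the point hangs on an unstated reading. Starting the clock at the biologic is an inference. From the first clinic visit, a child with long earlier attendance would stay in, subject to the undefined clause on lost data. This stands, and it is why the point is conditional. It also shows that the start point must be written down, because two people extracting the same file could classify it differently.

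Second, the affected group may be small or empty. The disease is described as chronic, so a child who stops a biologic may well keep attending the eye clinic and be counted. This also stands. A reader might infer that children who discontinue because of reactions are dropped; item 4 does not say that.

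Third, item 5 also removes children who may have recorded harms, yet it is left alone here. That is true, but item 5 selects on information from before treatment, whereas item 4, on the reading at issue, selects on what happened afterwards. Leaving item 5 in place keeps the change small.

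Fourth, a reader might go further and ask for a censored time-to-event analysis, or a success rate that counts early leavers as failures. Neither follows. The plan is descriptive, and any lack of censoring touches retained patients equally. Adding only unfavourable exits as failures could move the success rate in one direction only. It could also override the plan's own definition of efficacy, which a child leaving early might already meet through a steroid reduction.

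**Conclusion.** The point holds as a conditional one. Item 4 is study-wide, one group serves efficacy and harms, and no exception is made for adverse effects. If the 3 months run from the start of the biologic, reactions recorded in children who left follow-up earlier are not counted, in a study that sets out to weigh benefit against side effects.

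Its size cannot be stated. A reader might infer that the plan understates the adverse-effect rate or flatters the success rate. The documents do not support either: they do not show that any child left early after a reaction, and the difference e·(a − b) can take either sign. Nor is a minimum follow-up for the efficacy comparison at fault.

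The change is worth making because it corrects a stated rule that bears on a stated aim, at low cost. The conclusion rests on two assumptions: that the clock starts with the biologic, and that at least some excluded files contain a record after that start.

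**What to change.** 1. In item 4, state that the 3 months run from the start of the biologic.
2. Apply item 4 only to the pre/post efficacy comparison.
3. Report adverse effects and their time of onset in every otherwise eligible patient (all other inclusion and exclusion criteria unchanged, item 5 included) with a recorded biologic dose and any later record. Give each patient's length of follow-up, so that a short observation without an event is visible as such.
4. Report the number excluded from efficacy under item 4, by reason where recorded: late start, lost file, left after an adverse effect, left after inadequate control, unknown. Patients with no later record are counted here and are not treated as free of events.

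The cost is mainly wording, plus a reason-for-exclusion column and a length-of-follow-up column in the extraction sheet. No new data source is needed, since all JIA files are already to be reviewed. The downsides are that efficacy and safety denominators will differ and must be labelled, that some short or incomplete files enter the safety table, so that its percentages mix different lengths of observation, and that many reasons may prove to be unknown in a retrospective file review.

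### Exclusion item 4 makes the efficacious percentage conditional on staying in follow-up, and nothing in the plan shows how many children it removes or in which direction that moves the result

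*Combined protocol and SAP*

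**What the plan says.** The source population, under Population of study & disease condition, is a "Retrograde analysis of data of all patients presented to Aboul Reesh uveitis clinic taking biologics from January 2017- January 2020". Exclusion item 4 then removes "Patients without adequate duration for follow-up (less than 3 months) or lost follow up data". Item 5 deals separately with children whose records before the biologic are missing, so item 4 is most naturally read as follow-up after the biologic starts. The start of the 3-month clock is not stated.

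Efficacy is a yes/no result for each child. In Methodology: "Treatment was determined as efficacious if one of the following was fulfilled". The three criteria are "No relapses or decrease in the number of relapses", "Decrease in dose of topical or systemic steroids" and "Improvement of BCVA of at least two lines". Relapses are recorded as "Number of relapses in one year".

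The Statistical analysis plan summarises such results as "frequencies and percentages for categorical data". It names no denominator. Neither it nor the rest of the protocol has a rule for missing outcomes, a tally of children removed under item 4, a sensitivity analysis, or a method that censors short follow-up.

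**The concern.** A child enters the efficacy denominator only if follow-up after the start of treatment was long enough and the data survive. Both are settled after the biologic has begun, and either could be related to how well it worked. The percentage therefore estimates success among children who were retained, while a reader will naturally take it as success among children who were started on a biologic.

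There is no comparison group in which a similar loss could be seen, and no count of the children removed, so a reader of the results could not judge whether the two quantities are close or far apart.

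A second problem is one of wording. The lost-data clause is joined to the 3-month clause by an "or" in the sense of an alternative. Read literally, it could exclude a child who has ample usable visits and stopped attending only later. Two people abstracting files could apply it differently.

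**Working it through.** The plan states no efficacy rate, loss rate or calculated sample size to reproduce. The 250 under Sample size is a number of files to review. What can be done is to bound the effect of the shortened denominator.

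**Inputs (all assumed, because the documents give none)**
- S: proportion efficacious among children retained under item 4.
- L: proportion of otherwise eligible starters removed by item 4.
- s: proportion efficacious among those removed, which is not observed.

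**Formulas**
- All-starter proportion = S(1 − L) + sL.
- Bias of the reported figure = S − [S(1 − L) + sL] = L(S − s).
- Lower bound (s = 0): S(1 − L). Upper bound (s = 1): S(1 − L) + L.

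**Results: all-starter figure, with the bias of the reported figure in percentage points**

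| S | L | s = 0 | s = 20% | s = S | s = 100% |
|---|---|---|---|---|---|
| 80% | 5% | 76% (+4) | 77% (+3) | 80% (0) | 81% (−1) |
| 80% | 20% | 64% (+16) | 68% (+12) | 80% (0) | 84% (−4) |
| 70% | 30% | 49% (+21) | 55% (+15) | 70% (0) | 79% (−9) |

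For example, with S = 80% and L = 20%: 0.80 × 0.80 = 0.64 at s = 0; 0.64 + 0.20 × 0.20 = 0.68 at s = 20%; 0.64 + 0.20 = 0.84 at s = 100%.

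The sign of the bias is the sign of S − s. Nothing in the documents bears on s, so the sign is open. The greatest possible overstatement is L × S and the greatest possible understatement is L × (1 − S). When S is above 50% there is more room for overstatement, but that describes the bounds and is not evidence about where the truth lies.

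**The case against.** A minimum follow-up is a defensible choice in a retrospective file review, because response cannot be judged without some time on treatment. It also protects the endpoint: a child seen once after starting could meet the no-relapse criterion simply because there was no time to relapse. This stands, and it is why the 3-month analysis should remain the main one.

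A reader might infer that the reported percentage is likely too high, because children leave when a drug fails them. The documents do not support that. They give no reasons for loss, and other routes are open. The study period ends in January 2020 and the protocol is dated 1 March 2020, so late starters may have under 3 months for purely administrative reasons. Lost data may mean lost records. Children who are doing well may stop attending. The first two need not be related to outcome, and the third would push the figure down.

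A reader might also take the efficacious percentage to be the study's main benefit figure. No primary endpoint is named. The stated aims are control of inflammation, prevention of sight-threatening complications and the balance against side effects, and tests on other measures are planned. The percentage follows from the yes/no definition, but its rank does not.

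Finally, the lost-data clause can be read more mildly, as follow-up data that are simply unavailable, in parallel with item 5. That reading is reasonable. The wording allows both, so it needs clarifying whichever was meant.

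None of this supplies the missing count of children removed or any check on their effect.

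**Conclusion.** The point holds as one of design and reporting. Item 4 conditions the efficacious percentage on retention after treatment starts, and the plan neither counts the children removed nor tests what their removal does. The reported figure is too high if they did worse than those kept, too low if they did better, and unbiased if they did the same.

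The size cannot be given. With an assumed 80% efficacious among those retained, the effect is minor at 5% removed (all-starter range 76% to 81%) and material at 20% removed (64% to 84%). This rests on reading item 4 as follow-up after the biologic starts, and on the assumed rates. The point concerns the efficacy denominator only.

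**What to change.** 1. Reword item 4 so that a child with at least 3 months of usable visits after starting the biologic is kept, and is scored on those data even if lost later. State that the clock starts with the biologic, and give the data cut-off date.
2. Keep the 3-month analysis as the main one, but count every otherwise eligible child who started a biologic.
3. Report the number removed under item 4, split where the file allows into administrative (started under 3 months before the cut-off), missing records, and stopped attending.
4. Beside the 3-month percentage, give the all-starter percentage twice: with children lacking 3 months of data all counted as not efficacious, then all counted as efficacious. Present these as lower and upper bounds, not as estimates.
5. Do not score the no-relapse criterion as success in a child with under 3 months of follow-up.

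The cost is a change of protocol wording, a small tally while the files are being reviewed anyway, and a slightly longer results table. The reason for loss may not be recoverable from every file, so an unknown category will be needed. The lower figure may look less favourable.

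### Adverse effects are sought only in eye-clinic files, so they are likely to be under-counted relative to ocular benefit, which would favour biologics in the benefit-harm judgement

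*Combined protocol and SAP*

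**What the plan says.** **Data source.** The Methodology section describes a "retrospective analysis of all files of patients with JIA from the Abou El Reesh ophthalmology outpatient clinic". The Sample size section points the same way: "It is expected to review 250 patients files of Aboul Reesh uveitis clinic". The population is likewise defined through that clinic: "all patients presented to Aboul Reesh uveitis clinic taking biologics from January 2017- January 2020". No rheumatology, general paediatric, inpatient, laboratory, pharmacy or infusion record is named, and no contact with families.

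**Aim.** The Background and introduction ends by asking whether biologics control ocular inflammation and prevent sight-threatening complications, and "if this outweighs their potential associated side effects". The paragraph just before it describes immunosuppressive drugs: "They increase the susceptibility of children to infection, may cause organ toxicity, reversible bone marrow suppression", with possible malignancy added.

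**Harm variables.** The Methodology lists "adverse effects, and time taken to develop those adverse effects" among the treatment parameters. It does not say how adverse effects are defined, graded, attributed or looked for. The Statistical analysis plan has no analysis specific to adverse effects and no rule for weighing them against benefit.

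**The concern.** The two sides of the intended comparison are not observed with the same completeness. Visual acuity, cell grade, relapses and ocular complications are what an eye clinic examines and writes down. A serious infection or an abnormal blood count may be managed and recorded in another department, and nothing in the plan goes to look there.

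Events missed in this way reduce the harm side and leave the benefit side unchanged. Time to adverse effect is also exposed, because an onset date learned second-hand is less reliable than one taken from the record where the event was managed. Reviewing more eye files would narrow the confidence interval around the same under-count without correcting it.

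At stake is the benefit-harm statement. The efficacy summaries do not depend on this point.

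**Working it through.** **Figures in the plan.** There is none to reproduce. The 250 files are an expected review count. The documents give no adverse-effect rate, no share of systemic events that reach an eye file, and no number of children treated with biologics. All three are assumed below and shown over a range.

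**Step 1: observed rate.** Observed rate = true rate × share of events captured in the file.

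| True rate | 80% captured | 50% captured | 30% captured |
|---|---|---|---|
| 5% | 4% | 2.5% | 1.5% |
| 10% | 8% | 5% | 3% |
| 20% | 16% | 10% | 6% |

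**Step 2: a plausible range for the number of children.** The Background reports that JIA made up 39% of paediatric uveitis in a cohort from the same university's paediatric hospital. If that share applied to the 250 files, 250 × 0.39 = 97.5, so about 97 would be JIA files. Only those treated with biologics and meeting the other criteria are analysed, so the number would be smaller. I use 20, 40 and 60, with 97 as a ceiling under that assumption.

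**Step 3: chance of seeing no event.** P(none seen) = (1 − observed rate)^n. For a true rate of 10%:

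| Children | Full capture | 80% | 50% | 30% |
|---|---|---|---|---|
| 20 | 12.2% | 18.9% | 35.8% | 54.4% |
| 40 | 1.5% | 3.6% | 12.9% | 29.6% |
| 60 | 0.2% | 0.7% | 4.6% | 16.1% |
| 97 | <0.1% | <0.1% | 0.7% | 5.2% |

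For 40 children: 0.90^40 = 0.015 at full capture, 0.95^40 = 0.129 at 50%, and 0.97^40 = 0.296 at 30%. Expected events fall from 4.0 to 2.0 and 1.2.

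**Reading.** In a cohort of 20 to 40, incomplete capture makes a report of no adverse effects considerably more likely when the true rate is 10%. Near the ceiling of 97 a report of none is unlikely, but the rate is still under-stated in the same proportion.

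**The case against.** **The eye files may hold more systemic information than this point assumes.** The same files are expected to supply "Dose and frequency of systemic, regional and topical steroids" and the type, dose and duration of the biologic. The hospital's stated reasons for using biologics include intolerance of other drugs with severe reactions, which suggests that drug reactions are sometimes known to the clinic. This stands, and it is why the under-count is likely and not demonstrated. However, prescriptions and reasons for prescribing do not show that later systemic events are recorded completely, and the plan does not claim that they are.

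**The harm list is not about biologics.** It is written of immunosuppressive drugs as steroid-sparing agents, and the documents give no side-effect profile for biologics. This also stands. It is nevertheless the list of drug harms that leads directly into the aim.

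**Other errors could run the opposite way.** With no attribution rule, events due to co-medication could be counted against the biologic. This is possible, so the net direction of all errors together is not established. It does not restore events that were never found.

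**Stronger readings a reader might infer.**
- *A silent file will be counted as no adverse effect.* The plan states no rule for a missing entry, in either direction.
- *Systemic events reach the eye file only through a parent or a referral letter.* Nothing in the documents says so.
- *The same files cannot be trusted to confirm the JIA diagnosis.* The Exclusion criteria already remove patients without a definitive diagnosis, and that is a separate matter from adverse-effect capture.

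**Conclusion.** The point holds as a likely under-count. Every statement about where data come from leads to one clinic and no other source is added, while the aim needs a count of harms that may be recorded elsewhere. Followed as written, the plan observes ocular benefit directly and is likely to miss some adverse effects and some onset times, which would favour biologics in the benefit-harm judgement.

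The size is unknown. The illustration (10% seen as 5%, and the chance of no event rising from 1.5% to 12.9%) rests on three assumptions: a true rate of 10%, capture of 50%, and 40 children.

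Two further inferences should be resisted. A reader might conclude that capture must be close to complete before any comparison of benefit and harm is valid. The plan states no threshold or weighting rule, so no required capture level follows from it. A reader might also take the plan to assert that benefit outweighs side effects. It only poses this as a question. The consequence is that, with this source alone, the question should not be answered.

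**What to change.** **Preferred change.** For the included children only, a subset of the 250 files:
- Also extract adverse effects and their dates from the hospital's paediatric or rheumatology records, where these are accessible.
- Record for each child whether that second record was found.
- Report adverse effects twice: for all included children, and for those whose second record was found.

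**If those records are not accessible.** Restate the safety aim and conclusion as adverse effects noted in ophthalmology files, a minimum estimate, and draw no conclusion on whether benefit outweighs side effects.

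**Cost.** The preferred change needs a second chart look-up for the included children. The reported adverse-effect rate may be higher. The subset with a second record will be smaller and possibly selected, for instance towards sicker children or those managed within the hospital, which is why both denominators should be shown. The fallback costs only a change of wording, but it leaves the benefit-harm question unanswered.
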